ABSTRACT OF PROPOSED INVESTIGATION

Autism is a neurodevelopmental condition and presents as a distinct neurotype, characterised by a wide range of social and behavioural differences, including divergences in cognitive thinking and methods of communication [1]. Autism shares significant behavioural features with restrictive eating disorders (EDs) such as anorexia nervosa (AN). Those with AN exhibit significantly elevated levels of Autistic characteristics, ranging between 2%-53% [2-4]. Importantly, a characteristic shown by some Autistic people is the presence of masking, a term describing a strategy used by Autistic people, whether conscious or unconscious, to 'blend in' with neurotypical peers [5]. While initially overlooked, it is now well-known that masking behaviour can produce detrimental effects on Autistic individuals' mental health. The presence of masking behaviour has been associated with increased levels of physical and mental exhaustion [6,7], anxiety/depression [8], and importantly, an increased presence of EDs [5].

The Eating Disorder and Autism Collaborative (EDAC) [9] used an arts-based method called Photovoice to capture the experiences of Autistic individuals with lived/living experience of an ED. Participants commented on the how an ED can serve as a means to mask or camouflage within a neurotypical world (e.g., an Autistic person may use restrictive eating or excessive exercise as a means with which to 'fit in' with their peers). Magnetic resonance imaging (MRI) research can assist in understanding which regions of the brain are associated with masking behaviour, and whether there are differences in brain function/structure in Autistic individuals with versus without an ED.

This research aims to use a combination of brain imaging techniques and administration of scientifically validated questionnaires to investigate the relationship between autism, restrictive EDs, and masking. A 3T MRI scan will be used to investigate neuroanatomical and functional differences in Autistic individuals with AN (n=25) relative to healthy Autistic individuals (n=25), with questionnaires used to evaluate levels of Autistic characteristics, ED traits, as well as masking and social camouflage. Findings from this research aim to provide evidence towards the complexities of ED development and maintenance in Autistic individuals.

BACKGROUND

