Autism shares significant behavioural features with restrictive eating disorders (EDs), such as AN. Anorexia Nervosa (AN) is a severe and life-threatening eating disorder (ED) characterised by pathological fears of weight gain, a distorted body image, and extremely low body weight in relation to individual age and sex [1]. In Autistic people, masking has been associated with increased presentation of restrictive eating habits [5,7] and has been associated with poorer mental health. The presence of masking behaviour has been associated with increased levels of physical and mental exhaustion [6,7], anxiety, and depression [8].

Structural magnetic resonance imaging (MRI) research reports similarities in brain structure between those with AN and Autistic individuals, reporting differential structure of the amygdala [10,11], cerebellum [12,13], insula [14,15], cingulate cortex [14-16], as well as orbitofrontal and frontal cortex [15,16] in both groups. Shared differences extend to neuroanatomical parameters essential for brain development and connectivity [17], such as cortical thickness and surface area [18,19]. Further, there are no studies investigation structural correlates with masking behaviour, or distinct aspects of social camouflage such as masking, assimilation and compensation [20]. Further research is necessary to disentangle the complex relationship between Autistic characteristics and symptomatology associated with restrictive EDs.

We believe that by further understanding the brain structure and function associated with ED symptomatology and masking behaviour in Autistic individuals can assist with the development of novel or tailored interventions for EDs in this community.

STUDY AIMS AND OBJECTIVES

[figure not shown]
The main aims of the study are:

- 1) To examine whether Autistic individuals with AN exhibit differences in brain structure or function relative to Autistic individuals without AN.
- 2) To determine whether Autistic individuals with AN exhibit higher masking behaviour than Autistic individuals without AN.
- 3) To determine if there are associations between the levels of masking, ED symptomatology and brain structure in Autistic individuals.

Primary Objective

The primary objective of this study is to determine the relationship between masking, ED symptomatology and brain structure in Autistic individuals.

STUDY DESIGN

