Abbreviations: AQ – Autism Spectrum Quotient; ARI – Aberdeen Royal Infirmary; ED – Eating Disorder; EDAC – Eating Disorders and Autism Collaborative;

STUDY POPULATION

The target population for this study includes 25 healthy Autistic individuals and 25 Autistic individuals with AN (aged 25-45). This study will be focusing on an adult sample to ensure individuals are able to articulate longstanding experiences of masking and social camouflage. Participants must also have no contraindications to MRI and have no history of trauma affecting the brain.

INCLUSION CRITERIA

Study Phase 1

- Healthy Autistic Individuals (Autistic Controls) must:
 - Be aged 25-45 years
 - Be Autistic (clinically diagnosed and/or have an AQ-10 score of ≥ 6)
 - Be able to provide informed consent for the study
 - Be able to read, understand and respond to questionnaires in English
 - Have no history of an ED
 - Willing to have an MRI scan in Aberdeen
- Autistic Individuals with AN (Autistic individuals with AN) must:
 - Be aged 25-45 years
 - Be Autistic (clinically diagnosed and/or have an AQ-10 score of ≥ 6)
 - Be able to provide informed consent to the study
 - Be able to read, understand and respond to questionnaires in English
 - Have a diagnosis of AN or a BMI of < 18.5
 - Willing to have an MRI scan in Aberdeen

EXCLUSION CRITERIA

- Individuals are not eligible for the study if they:
 - Are aged < 25 or > 45 years
 - Are not Autistic or not clinically diagnosed as Autistic and have an AQ-10 score of < 6
 - Are diagnosed with an ED other than AN
 - Have a history of brain injury (e.g., stroke)
 - Be unable to provide informed consent for the study
 - Have contraindications to MRI scanning, such as implantable cardiac devices
 - Are unable to read, understand and respond to questionnaires in English
 - As participants will need to consent to the study and complete questionnaires by themselves, individuals with intellectual disability will be excluded from this study

The Autism Spectrum Quotient (AQ-10) is a short questionnaire that primary care practitioners can use to test if a person should be referred for an autism assessment. We will use this as a screening tool to confirm the presence of Autistic traits in addition to the presence of a clinical diagnosis.

PARTICIPANT SELECTION AND ENROLMENT

IDENTIFYING PARTICIPANTS FOR ELIGIBILITY

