Only eligible individuals (following our pre-defined inclusion/exclusion criteria) will continue with the rest of the study procedures. Participants who are not eligible will not be recruited into the study. Individuals will complete a pre-recruitment screening survey. The link to this screening survey will be sent to potential participants who have expressed an interest in taking part in the study, and will be completed by all potential participants. If 1) participants complete the pre-recruitment screener and are not eligible to participate or 2) participants are deemed eligible but the recruitment limit of n=50 has been reached, they will be informed that they will not be able to take part, and will be thanked for their time and interest. Non-eligible individuals will also be made aware that the data they have provided and their contact details will be deleted.

WITHDRAWAL PROCEDURES

Participants are free to withdraw at any time during the study without having to give a reason. Should this occur, additional participants will be recruited until the required study target number is achieved. Data collected with consent would be retained and used in the study. No further data would be collected or any other research procedures carried out on the participant.

STUDY ASSESSMENTS

Questionnaires (either online or in-person): To be completed by all participants.

- A demographic questionnaire that will be used to collect information on gender, age, height and weight, education level, employment status, time since and quality of autism diagnosis, co-occurring physical, mental health or psychological conditions, co-occurring EDs and duration of ED illness, as well as current medication status.
- The Eating Disorder Examination Questionnaire (EDE-Q; [21]) will be used to evaluate the presence, frequency and severity of eating disorder symptoms.
- The 10-item Autism Spectrum Quotient (AQ-10; [22]) will be used to examine Autistic characteristics. The AQ-10 will also be used to screen for ingenuine participants.
- Presence and levels of monotropism or selective interests will be evaluated using the Monotropism Questionnaire (MQ; [23]).

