Risks associated with use of MRI: Magnetic resonance imaging is a safe, non-invasive procedure and there are no known side effects to receiving an MRI scan. However, if there is any indication or potential with which an individual may be pregnant, they will not be considered eligible for the study. This information will be collected on the MRI safety screener before an individual receives their scan.

SAMPLE SIZE

Sample size calculations are not appropriate for pilot studies. Our sample size of 25 for each group will ensure a spread of measurements to effectively estimate effect sizes and aid planning for future studies.

DATA COLLECTION

All research activities, methods of data collection and analysis associated with the proposed project will be conducted in accordance with the UK data protection laws.

All online data collection for this project will be conducted using Qualtrics (<https://www.qualtrics.com/en-gb>), a secure online survey platform. Qualtrics will facilitate efficient data gathering, enabling participants to complete the questionnaires remotely with a variety of accessibility options and at their own convenience. If participants opt to complete questionnaires during their in-person visit, all data will be provided on paper, and will be transposed to an Excel spreadsheet securely stored on University of Aberdeen servers via a University OneDrive folder. Electronic consent forms will also be securely stored on a separate excel spreadsheet on a University OneDrive folder. The paper copies of both questionnaires and informed consent will be retained and stored securely in locked cabinets within [name], made only accessible to the research team. Subject logs will also be retained as an Excel spreadsheet and stored on a separate secure University OneDrive folder. MRI scans will also be stored on a secure OneDrive folder, with statistics from scans transposed to an Excel spreadsheet. Once participant MRI scans have been linked to participant questionnaire responses and their consent, research data will contain ID numbers for each participant which will be pseudoanonymised. The index linking pseudoanonymised IDs to participants' names will be stored in a separate, secure excel spreadsheet within a University of Aberdeen OneDrive folder, made only accessible to the PI ([name]).

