Published results will not contain any personal data that could allow identification of individual participants.

PROPOSED ANALYSES

Methods of analysis will include assessment of demographic characteristics, brain structure and functional connectivity patterns, as well as calculation of generalised linear models between characteristics of masking and brain structure, as well as between characteristics of masking and symptoms of eating disorders. Pre-processing of MRI scans will utilise the FreeSurfer and fMRIprep software packages for brain structure and function respectively. Regions of interests (ROIs) will be derived from normalisation to the standard Desikan-Killiany atlas. All statistical analyses will be conducted using the R Software.

To achieve aim 1, structural differences of brain regions, both global and specific ROIs, will be reported as mean \pm standard deviation (in mm³) for each ROI between groups. For functional differences an independent component analysis approach will be used via the CONN toolbox on the statistical parametric mapping (SPM) software package, reported in Z-scores for incorporated components, and means \pm standard deviations of component loadings. Neuroimaging-based findings will also be accompanied by determining any group-based differences across demographic and questionnaire-derived information.

To achieve aim 2, mean differences on scores derived from the CAT-Q will be compared across groups and will be reported as mean \pm standard deviation.

To achieve aim 3, linear models will be used to evaluate associations between brain structure and function and domains of social camouflage (particularly masking behaviour), as well as associations between levels of masking and the presence of reported anxiety, depression, work and social adjustment and trauma. A 3-path mediation model will also assess whether ROI-based brain structure mediates the relationship between masking behaviour and ED symptomatology within the entire sample.

The statistical analysis will be conducted by the Chief Investigator (CI; [name]), and an Autistic peer researcher and PhD student ([name]). The statistical plan was developed by the CI and [name].

MISSING DATA

Where appropriate, missing data will be imputed to minimise the loss of data. Depending on the type of data missing, either simple imputation, multiple imputation will be used to minimise data loss.

EARLY STOPPING

No interim analysis is planned to inform early stopping.

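### Aim 2 compares CAT-Q means between two unmatched, non-randomised groups without using the gender and age data collected on everyone, so an imbalance would stay in the reported difference

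*Protocol*

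**What the plan says.** Aim 2, under STUDY AIMS AND OBJECTIVES, is "To determine whether Autistic individuals with AN exhibit higher masking behaviour than Autistic individuals without AN". Under PROPOSED ANALYSES the method is that "mean differences on scores derived from the CAT-Q will be compared across groups", reported as mean and standard deviation. No covariate is named. In the same section, linear models are named for aim 3 (masking with brain measures and with mental-health scores), but not for the AN-versus-control contrast.

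The groups are 25 and 25, both aged 25-45 (STUDY POPULATION). Nothing in the eligibility or recruitment sections matches or balances them on gender or age. Some recruitment routes are shared: A-ND, SWAN, the EDAC network and public advertising. Others are not: controls are also sought through the University of Aberdeen's Neurodiversity Network, and the AN group through the NHS Grampian eating disorders service, NEEDS and BEAT.

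Under STUDY ASSESSMENTS, a questionnaire given to all participants will "collect information on gender, age, height and weight, education level, employment status, time since and quality of autism diagnosis" and further items. AQ-10 is also completed by everyone.

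Two statements bear on balance. PROPOSED ANALYSES opens with a general assessment of demographic characteristics. Under aim 1 it adds: "Neuroimaging-based findings will also be accompanied by determining any group-based differences across demographic and questionnaire-derived information". Neither feeds into the CAT-Q contrast.

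**The concern.** A raw difference in means between self-selected groups combines whatever is associated with AN with whatever else differs between the people who volunteered. If gender or age is related to CAT-Q score and its distribution differs between the groups, part of the difference reflects who was recruited. Describing the imbalance in a table tells the reader that the problem exists but leaves the estimate unchanged.

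This matters even in a pilot. The SAMPLE SIZE section justifies 25 per group by the need to estimate effect sizes for planning later work. Confounding bias does not shrink as the sample grows, so a distorted estimate here would go straight into the planning of the next study. The covariates needed to reduce it are already being collected.

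**Working it through.** The protocol states no alpha, power, SD or expected difference ("Sample size calculations are not appropriate for pilot studies"), so there is no figure of its own to reproduce. All covariate effects and imbalances below are assumptions, shown as ranges. Units are within-group SDs of the CAT-Q score.

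**1. Precision of the stated contrast.** SE = sqrt(2/25) = 0.283 SD. With 48 degrees of freedom the 95% CI half-width is about 0.57 SD.

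**2. Bias from gender alone.** Bias = (gender difference in CAT-Q) × (difference between groups in proportion of women). The last column is the chance of a two-sided 5% result when AN has no effect, from the non-central t with 48 df.

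| Gender effect (SD) | Imbalance | Bias (SD) | Chance of p < 0.05 |
|---|---|---|---|
| 0.3 | 0.20 | 0.06 | 5.5% |
| 0.3 | 0.40 | 0.12 | 7.0% |
| 0.5 | 0.30 | 0.15 | 8.1% |
| 0.5 | 0.40 | 0.20 | 10.7% |
| 0.8 | 0.30 | 0.24 | 13.2% |
| 0.8 | 0.40 | 0.32 | 19.8% |

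A second set of assumptions, 95% women in the AN group against 60-70% in controls with a gender effect of 0.3-0.6 SD, gives 0.25 × 0.3 = 0.075 to 0.35 × 0.6 = 0.21 SD.

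**3. Simulation with no true AN effect** (25 v 25, 4,000 runs each). The adjusted model contained group, gender, age and AQ-10.

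| Case | Unadjusted difference; rejection rate | Adjusted difference; rejection rate | Mean SE, unadjusted to adjusted |
|---|---|---|---|
| Gender effect 0.5, 90% v 60% women, AQ-10 slope 0.3, no AQ-10 shift | 0.15 SD; 8% | 0.00 SD; 5% | 0.286 to 0.295 |
| Same, with AQ-10 shift 0.5 SD | 0.31 SD; 18% | 0.00 SD; 5% | 0.288 to 0.305 |
| Gender effect 0.8, 90% v 50% women, AQ-10 slope 0.4, shift 0.5 SD | 0.52 SD; 41% | 0.00 SD; 5% | 0.297 to 0.306 |

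In the second and third cases part of the bias comes from the assumed AQ-10 shift (0.3 × 0.5 = 0.15 and 0.4 × 0.5 = 0.20 SD). A model with gender and age only would leave that part in place.

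**4. Cost of adjustment.** The SE ratios are 0.295/0.286 = 1.03, 0.305/0.288 = 1.06 and 0.306/0.297 = 1.03, a rise of about 3-6%. With gender coded in two categories, gender and age reduce the residual degrees of freedom from 48 to 46, and adding AQ-10 to 45.

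**The case against.** The strongest reply is that the aim 2 sentence sets a reporting format, never says unadjusted, and leaves covariates to an analysis plan that is not shown. This has some force. But the protocol does name a method for aim 2, and names linear models only for aim 3, so the natural reading is a plain comparison of means.

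A second reply is that aim 2 is descriptive: a raw difference properly answers whether one group scores higher. That stands, and is the reason to keep the raw means and SDs. The difficulty starts when the difference is attributed to AN or carried forward as a planning effect size.

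Third, no imbalance is documented. That also stands. Shared recruitment, including through SWAN, may narrow any gender gap, and the common 25-45 range limits age differences. The rejection rates above also presume a two-sided 5% test that the protocol never specifies, and the stated Primary Objective is not this contrast.

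Four stronger readings are tempting but unsupported:

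- A reader might infer that the AN group will have higher AQ-10 scores, because the abstract says "Those with AN exhibit significantly elevated levels of Autistic characteristics". That sentence describes people with AN in general. Here both groups must be Autistic under the same criterion.
- A reader might infer that the only balance check belongs to the imaging results. The opening of PROPOSED ANALYSES plans a general demographic assessment.
- A reader might infer that adjustment would gain precision. Under the simulated imbalances the SE rises.
- A reader might infer that the AQ-10-adjusted difference should be the main result. AQ-10 is part of the entry criteria and may be bound up with masking, so adjusting for it changes the question.

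**Conclusion.** The point holds as a limited one about the stated analysis. The aim 2 contrast does not use gender and age, although the groups are unmatched and partly recruited from different places. The planned demographic assessment would show an imbalance but not correct for it.

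The documents fix neither the size nor the direction of any bias. Under the assumed ranges, gender alone contributes from about 0.06-0.08 SD, which is negligible, to about 0.2-0.3 SD, which is close to the SE of 0.28 SD. The larger simulated distortions (0.31 and 0.52 SD) also require an assumed AQ-10 difference and should not be read as forecasts. Age is the weaker of the two covariates because of the shared age range. The case rests on bias alone.

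**What to change.** State the aim 2 analysis as a linear model of the CAT-Q score on group, with gender and age as covariates. Report the adjusted AN-minus-control difference with its 95% CI beside the raw group means and SDs. Show a second model adding AQ-10 as a sensitivity analysis, described as the difference at the same trait level. Say in advance how gender categories will be grouped, since some may be sparse at 25 per group.

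The cost is a sentence or two of analysis text, a few degrees of freedom and, if the groups are imbalanced, a slightly larger SE (about 3-6% in the simulated cases, which included AQ-10). No new data are needed. Adjustment for gender and age does not deal with unmeasured differences between volunteers, and the report should say so.
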